#### **8.4.2 Vital Signs**

Vital signs will be measured at all clinic visits as specified in the Schedule of Events (Section 8.1). Vital sign measurements will include blood pressure (systolic and diastolic, mmHg), and pulse rate (beats per minute), aural/oral temperature (°C), and respiration rate (breaths per minute). All measurements will be obtained after the subject has been resting supine for at least 5 minutes.

#### **8.4.3 Laboratory Assessments**

Laboratory testing will be performed at clinic visits as specified in the Schedule of Events (Section 8.1). Any unused duplicated samples collected for the purpose of this study will be destroyed after the completion of the study.

#### **8.4.3.1 Hematology**

Samples for hematology assessments will be obtained during Screening, within 72 hours prior to LYR-210 administration/sham procedure, and at Weeks 4 and 12, Week 24/EOT, and Week 28 visits as specified in the Schedule of Events (Section 8.1).

Hematology assessments will include a leukocyte count with differential (neutrophils, eosinophils, lymphocytes, monocytes, and basophils), erythrocytes, hematocrit, hemoglobin, and platelet count.

Testing will be performed according to the standard of care at the investigational site.

#### **8.4.3.2 Blood Chemistry**

Samples for blood chemistry assessments will be obtained during Screening, within 72 hours prior to LYR-210 administration/sham procedure, and at Weeks 4 and 12, Week 24/EOT, and Week 28 visits as specified in the Schedule of Events (Section 8.1).

Clinical blood chemistry laboratory analytes will include electrolytes (sodium, potassium, chloride, and bicarbonate), blood urea nitrogen, serum creatinine, glucose, total bilirubin, aspartate aminotransferase, alanine aminotransferase, alkaline phosphatase, lactate dehydrogenase, uric acid, total protein, albumin, calcium, magnesium, and phosphate.

Testing will be performed according to the standard of care at the investigational site unless otherwise noted in the Lab Manual.

#### **8.4.3.3 Morning Serum Cortisol**

Samples for serum cortisol will be collected during the morning hours before 10:00 (i.e., before 1000 HRS) during Screening, within 72 hours prior to LYR-210 administration/sham procedure, and at Weeks 4 and 12, Week 24/EOT, and Week 28 visits as specified in the Schedule of Events (Section 8.1).

All serum cortisol samples, except for Screening, will be sent to a central laboratory for testing.

#### **8.4.4 Nasal Endoscopy Assessments**

Nasal cavities will be assessed by endoscopy on Day 1 before the LYR-210 administration/sham procedure, and at Weeks 2, 4 and 12, Week 24/EOT, and Week 28 visits as specified in the Schedule of Events (Section 8.1). Local nasal safety evaluation will be performed at these visits to document presence of epistaxis, mucosal erosion or ulceration, perforation, infection, and any other adverse local nasal observations.

#### **8.4.5 Ophthalmologic Assessments**

The ophthalmologic assessment of IOP and slit-lamp examination to identify cataract development will be conducted at Screening, Week 24/EOT, and Week 48/EOS visits as specified in the Schedule of Events (Section 8.1). IOP assessment will also be performed at Weeks 4 and 12 visits.

Assessments will be conducted by a blinded ophthalmologist/optometrist.

#### **8.4.6 Pharmacokinetic Analysis**

Blood samples for assessment of plasma PK will be at Day 1, Weeks 4 and 12, Week 24/EOT, and Week 28 visits as specified in the Schedule of Events (Section 8.1). [REDACTED]

At the Day 1 visit, the blood sample for plasma PK analysis will be collected prior to the LYR-210 administration/sham procedure. Subsequent blood samples may be collected at any time of the day during the scheduled study visits.

The concentration of MF in plasma will be measured at a central core lab.

#### **8.4.8 Pregnancy or Breast Feeding**

Females of child-bearing potential must test negative for pregnancy at the time of Screening visit based on a serum pregnancy test and re-verified prior to randomization at Day 1 visit based on a urine pregnancy test. Females who can confirm that they are surgically sterile or have been postmenopausal for at least 1 year prior to signing the ICF do not need to undergo a pregnancy test. Urine pregnancy test will be performed to successfully enrolled female subjects of child-bearing potential every 4 weeks during the treatment stage.

Female subjects who are of childbearing potential are required to practice a highly effective form of birth control to continue in the study and for 4 weeks after the removal procedure. Male subjects of reproductive potential who are having intercourse with female partners of childbearing potential must agree to use 2 forms of contraception, 1 of which must be a barrier method, during the study and for 4 weeks after the removal procedure. Acceptable barrier methods include a condom and diaphragm.

Definition of Childbearing Potential and Highly Effective Contraceptive Methods:

A woman is considered of childbearing potential (i.e., fertile), following menarche and until becoming post-menopausal unless permanently sterile. Permanent sterilization methods include hysterectomy, bilateral salpingectomy, and bilateral oophorectomy.

A post-menopausal state is defined as no menses for 12 months without an alternative medical cause. A high follicle stimulating hormone (FSH) level in the post-menopausal range may be used to confirm a post-menopausal state in women not using hormonal contraception or hormonal replacement therapy. However, in the absence of 12 months of amenorrhea, a single FSH measurement is insufficient.

For women of childbearing potential, the following methods of contraception, when used consistently and correctly, are considered reliable for participation in the study:

- Combined (estrogen and progestogen containing) hormonal contraception associated with inhibition of ovulation: oral, intravaginal, or transdermal
- Progestogen-only hormonal contraception associated with inhibition of ovulation: oral, injectable or implantable
- Intrauterine device (IUD)
- Intrauterine hormone-releasing system (IUS)
- Bilateral tubal; occlusion
- Vasectomized partner (provided that partner is the sole sexual partner and that vasectomized partner has received medical assessment of the surgical success)
- Sexual abstinence (refraining from heterosexual intercourse during the entire study period; the reliability of sexual abstinence needs to be evaluated in relation to the duration of the clinical study and the preferred and usual lifestyle of the subject).

If a female subject who has successfully received bilateral placement of either dose of the LYR-210 becomes pregnant during the treatment stage, the Investigator must notify the Sponsor within 24 hours of becoming aware of the event on a Pregnancy Report Form. The Investigator must continue to follow the pregnancy until the completion of the pregnancy, including the outcome and the condition of the newborn at 8 weeks post-partum (if applicable). If not all information on the Pregnancy Report Form is available at the time of the initial report, follow-up reports should be provided to the Sponsor in a timely manner. Additional subsequent follow-up is not needed when a newborn baby is healthy.

#### **8.4.9 Adverse Events and Serious Adverse Events**

##### **8.4.9.1 Adverse Event (AE)**

Throughout the course of the study, all efforts will be made to remain alert to possible AEs or untoward findings. If AEs occur, the first concern will be the safety and welfare of the subject. Appropriate medical intervention will be undertaken. Any AE observed by the Investigator or reported by the subjects, whether or not ascribed to the investigational procedure or product, will be recorded on the subject's AE Case Report Form. A new AE Case Report Form will be used for each AE. All on-going AEs that result in early termination from the study or are deemed to be study

product or procedure related by the Site Investigator will be followed up until resolution or stabilization of the AE.

Documentation regarding the AE should be made as to the nature, date of onset, end date, severity, and relationship to study drug, action(s) taken, seriousness, and outcome of any sign or symptom observed by the physician or reported by the subject upon indirect questioning.

An **AE** is any untoward medical occurrence (signs, symptoms, abnormal laboratory findings) in a subject regardless of relationship to the investigational product or procedure. Each adverse event is considered to be either expected or unexpected as described below. The site is required to report AEs that occur in the study. These events shall also be classified according to the suspected causality by the study Investigator.

A **Treatment Emergent AE (TEAE)** is an AE that occurs or worsens on or after initiation of the LYR-210 administration/sham procedure.

#### **8.4.9.2 Serious Adverse Event (SAE)**

An SAE is any untoward medical occurrence that:

- Results in, leads to, or contributes to, a death;
- Is life-threatening (“Life-threatening” refers to an event in which the subject was at risk of death at the time of the event. It does not refer to an event which hypothetically might have caused death if it were more severe);
- Results in subject hospitalization or prolongation of existing hospitalization;
- Results in persistent or significant disability/incapacity (i.e., permanent impairment of a body function or permanent damage to a body structure);
- Results in fetal distress, fetal death or a congenital anomaly/birth defect;
- Is an important medical event which may jeopardize the subject and may require medical or surgical intervention to prevent one of the above outcomes.

The Investigator will assess each AE for its seriousness. Please note the term “serious” AE is not synonymous with a “severe” AE, which may be used to describe the intensity of an event experienced by the subject (Section 8.4.9.4). Any treatment related SAE (Section 8.4.9.5) will be followed until resolution of the event, or until the subjects withdraw from the study.

#### **8.4.9.3 Relationship to Study Drug Product and Procedure**

The Investigator should initially classify the causality of an AE and determine the relationship between an AE and the study product or procedure.

#### 8.4.9.3.1 Relationship to Study Drug Product

The relationship between an AE and the LYR-210 study drug product will be determined by the Investigator on the basis of his or her clinical judgment and the following definitions:

- **Definitely Related:** The AE follows a reasonable temporal sequence from administration of the investigational product; the AE follows a known or expected response pattern to the investigational product.
- **Possibly Related:** The AE follows a reasonable temporal sequence from administration of the investigational product; the AE follows a known or expected response pattern to the investigational product but could readily have been produced by a number of other factors.
- **Not Related:** An AE for which sufficient information exists to indicate that the etiology is unrelated to the investigational product. One or more of the following variables apply:
  - The AE does not follow a reasonable temporal sequence following administration of the investigational product;
  - The AE is readily explained by the subject's clinical state or other therapies.

For events that are determined to be definitely or possibly related, additional information on the timing of the event in relation to the LYR-210 study drug product administration will be captured.

#### 8.4.9.3.2 Relationship to Study Procedure

The Relationship between an AE and the LYR-210 administration/sham procedure (within 24 hours) will be determined by the Investigator on the basis of his or her clinical judgment and the following definitions:

- **Definitely Related:** The AE follows a reasonable temporal sequence from performance of the study procedure; the AE follows a known or expected response pattern to the study procedure.
- **Possibly Related:** The AE follows a reasonable temporal sequence from performance of the study procedure; the AE follows a known or expected response pattern to the study procedure but could readily have been produced by a number of other factors.
- **Not Related:** An AE for which sufficient information exists to indicate that the etiology is unrelated to the study procedure. One or more of the following variables apply:
  - The AE does not follow a reasonable temporal sequence following the study procedure;
  - The AE is readily explained by the subject's clinical state or other therapies.

For events that are determined to be definitely or possibly related to the study LYR-210 administration/sham procedure, additional information on the timing of the event in relation to the study procedure will be captured.

#### **8.4.9.4 Severity of Adverse Events**

Severity of an AE is defined as a qualitative assessment of the degree of intensity of an adverse event as determined by the Investigator or reported to him/her by the subject. The assessment of severity is made irrespective of relationship to study procedure or product or seriousness of the event and should be evaluated according to the following scale:

- **Mild:** Event is noticeable to the subject but is easily tolerated and does not interfere with the subject's daily activities.
- **Moderate:** Event is bothersome, possibly requiring additional therapy, and may interfere with the subject's daily activities.
- **Severe:** Event is intolerable, necessitates additional therapy or alteration of therapy, and interferes with the subject's daily activities.

#### **8.4.9.5 Expectedness of Serious Adverse Events**

The expectedness of a product or procedure related SAE should be determined by Sponsor based upon existing safety information about the investigation product or study procedure using these explanations:

- **Unexpected:** An SAE that is not listed in the study protocol, Investigator's brochure, or prescribing information for the registered formulation of MF or is not listed at the specificity or severity that has been observed.
- **Expected:** An SAE that is listed in the Investigator's Brochure (IB) or prescribing information for the registered formulation of MF or is listed at the specificity and severity that has been observed.

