#### **8.4.9.6.3 Expedited Reporting**

Any serious and unexpected suspected adverse reactions (SUSARs) and unexpected adverse device effect (UADE) will be reported by the Sponsor or designee to the appropriate Regulatory Authorities in accordance with applicable local guidelines.

The SUSARs meet all the following criteria:

- Suspected adverse reaction
- Serious
- Unexpected
- Assessed as related to study treatment

A UADE is any serious adverse effect on health or safety, any life-threatening problem or death caused by, or associated with a device, if that effect, problem, or death was not previously identified in nature, severity, or degree of incidence in the application; or any other unanticipated serious problem associated with a device that relates to the rights, safety, or welfare of subjects.

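### The SAE expectedness definitions overlap: a related SAE listed in the IB or mometasone prescribing information, but not as observed, is both Expected and Unexpected

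*Protocol*

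**What the plan says.** Protocol Section 8.4.9.5 assigns the decision to the sponsor. Expectedness of a product- or procedure-related SAE "should be determined by Sponsor based upon existing safety information about the investigation product or study procedure using these explanations". Two definitions follow, each with two limbs joined by *or*.

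- Unexpected, first limb: "An SAE that is not listed in the study protocol, Investigator's brochure, or prescribing information for the registered formulation of MF". Second limb: "or is not listed at the specificity or severity that has been observed".
- Expected, first limb: "An SAE that is listed in the Investigator's Brochure (IB) or prescribing information for the registered formulation of MF". Second limb: "or is listed at the specificity and severity that has been observed". Where the two limbs of Expected join, the text runs "prescribing information for the registered formulation of MF or is listed at the specificity and severity that has been observed".

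Section 8.4.9.6.3 then sets the expedited-reporting rule. "The SUSARs meet all the following criteria", and being unexpected is one of the four criteria listed. The same section has a separate route for unexpected adverse device effects (UADEs). Neither the protocol nor the SAP says which definition prevails when both apply, and the SAP does not deal with expectedness.

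**The concern.** The two definitions are meant to split related SAEs into two classes, and the split feeds directly into expedited reporting. As worded, they do not split them. The second limb of Unexpected catches a listed event whose observed form does not match the listing. The first limb of Expected takes in the same event, because it asks only for a listing and sets no condition on severity or specificity. In Expected, the match is an alternative to being listed, when it would need to be a further condition.

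At stake is a known type of reaction in a worse or more specific form than the reference documents describe. Such an event is serious and related. Whether it is a SUSAR depends on which of two equally applicable sentences the assessor reads. The matter is live in this trial because the reference sources include prescribing information for mometasone products other than this 24-week depot, and Section 2.3 describes Phase I experience with the 2500 µg depot only, in 20 subjects.

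The source lists also differ. The study protocol is named under Unexpected but not under Expected.

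**Working it through.** There is no figure in the plan to reproduce. The check is to list every feasible combination and apply both definitions literally.

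Inputs, all from Section 8.4.9.5:

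- P = 1 if the event is listed in the study protocol.
- B = 1 if it is listed in the IB or the mometasone prescribing information.
- M = 1 if it is listed, in any named source, at the observed specificity and severity. M = 1 requires P = 1 or B = 1.

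Rules:

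- Unexpected = not (P or B), or not M.
- Expected as written = B or M. The second limb names no source, so a match in any source satisfies it.
- Expected with *or* changed to *and* only = B and M.
- Expected with *and* plus a common source list = (P or B) and M.

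Three yes/no items give 2 × 2 × 2 = 8 combinations. One (P = 0, B = 0, M = 1) is impossible, which leaves 7.

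| Case | P | B | M | Unexpected | Expected as written | Expected, *and* only | Expected, *and* + same sources |
|---|---|---|---|---|---|---|---|
| 1 | 0 | 0 | 0 | yes | no | no | no |
| 2 | 0 | 1 | 0 | yes | **yes** | no | no |
| 3 | 0 | 1 | 1 | no | yes | yes | yes |
| 4 | 1 | 0 | 0 | yes | no | no | no |
| 5 | 1 | 0 | 1 | no | yes | **no** | yes |
| 6 | 1 | 1 | 0 | yes | **yes** | no | no |
| 7 | 1 | 1 | 1 | no | yes | yes | yes |

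Results:

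- As written, cases 2 and 6 (2 of 7) fall in both classes. In both, the event is listed in the IB or prescribing information but not as observed. The other 5 cases get exactly one class.
- An event listed only in the protocol and not as observed (case 4) is Unexpected only. The overlap therefore needs a listing in the IB or prescribing information.
- A mismatch in specificity triggers the overlap just as a mismatch in severity does.
- Changing *or* to *and* alone removes the overlap but leaves case 5 in neither class.
- Changing *or* to *and* and aligning the sources puts all 7 cases in exactly one class.

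Consequence under Section 8.4.9.6.3: a serious, related event in case 2 or 6 satisfies the SUSAR criterion of being unexpected if the first definition is used, and fails it if the second is used.

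**The case against.** The strongest reply is that this is a drafting slip. Unexpected is worded as the negation of a match, so the *or* in Expected was almost certainly meant as *and*, and an experienced safety team would read it that way. Other text also limits the harm. Section 8.4.9.6.2 has the sponsor report SAEs as local regulations require, and Section 8.4.9.6.3 defers to local guidelines. The UADE definition turns on whether a device effect's nature, severity or frequency was already identified, and LYR-210 is a combination product. Section 11.1 commits the study to GCP and applicable regulation, and there is DMC and medical-monitor review.

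Most of this stands as mitigation. None of it states which class applies to a drug-related SAE under Section 8.4.9.5, and a probable slip in an operative rule is a reason to correct it.

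Three stronger readings are tempting, and the documents do not support them.

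- A reader might infer that worse-than-listed SAEs will go unexpedited. The same event squarely meets Unexpected, nothing says that Expected prevails, and the UADE and local-rule routes remain. A missed SUSAR is possible, not the stated outcome.
- A reader might infer from the differing source lists that an event listed only in the protocol, at the observed severity, currently meets neither definition. The second limb of Expected names no source, so on its wording that event is Expected (case 5). A gap exists today only if one reads into that limb a source restriction that it does not state.
- A reader might infer that many events are exposed, for example local, ocular or adrenal ones. That depends on what the IB and the prescribing information list, and at what severity. Neither is among the documents.

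**Conclusion.** The wording of Section 8.4.9.5 is wrong as it stands. The two classes are not mutually exclusive for a related SAE listed in the IB or mometasone prescribing information but not at the observed specificity or severity. There is no tie-break, and the class decides SUSAR status, so such an event could be treated as expected and not expedited as a SUSAR.

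The size is 2 of 7 feasible listing patterns. That is a count of logical cases, not a frequency; how many events would be affected cannot be derived from the documents. The result rests on reading the two definitions literally and on finding no overriding rule elsewhere in the protocol or SAP. It concerns safety reporting only. Endpoints, analysis sets, sample size and error rates are untouched.

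**What to change.** Reword Expected so that both conditions must hold: the SAE is listed in the named reference safety information *and* is consistent with the specificity and severity listed there. Name the same reference document or documents in both definitions, so that Unexpected is the exact complement.

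Make the two changes together. Changing only the conjunction would create a gap for an event listed solely in the protocol at the observed severity.

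The cost is a one-sentence correction to the protocol and safety plan, with at most a few more expedited reports.

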#### **8.4.9.6 Reporting**

##### **8.4.9.6.1 Adverse Event Reporting**

Adverse events are to be collected from the time a subject signs informed consent until the completion of all follow-up visits. At each office visit during the study, AEs that have occurred since the previous office visit must be recorded. All subjects will be evaluated for AEs or complications associated with the study procedure or the investigational product. The Investigator will determine the severity and relationship of each event, as defined above.

AEs observed during the course of this study, regardless of severity or relationship to the study procedure or investigational product will be recorded on the appropriate CRF.

Documentation of all new AEs or changes in previously reported AEs will be recorded. Pre-existing diseases or conditions will not be reported as AEs unless there has been a substantial increase in severity or frequency of the problem which cannot be attributed to the expected progression of the disease or condition.

The Investigator will review the results of all clinical and laboratory tests as they become available. For each laboratory test result, the Investigator will ascertain whether the result represents an abnormal (e.g., clinically significant) change from Baseline for that individual subject. If this laboratory test result is determined to be an abnormal change from Baseline for that subject, the value will be considered to be an AE.

The description of the AE will include the date of onset, date of resolution (ongoing), severity, seriousness, relationship of the event to the investigational product and to the study procedure, and any procedure required. Specific procedures implemented in response to the AE will also be recorded. For all AEs, the Investigator is required to supply any additional data that may be deemed necessary by the Sponsor or designee.

All AEs will be coded using the latest version of Medical Dictionary for Regulatory Activities (MedDRA) throughout the study (Version 21.1 will be used at the start of the study).

